7.1 Primary Objective

To assess the safety of SCE therapy in patients with T1D.

7.2 Secondary Objectives

- 7.2.1 To assess the feasibility of SCE therapy in patients with T1D
- 7.2.2 To evaluate preliminary efficacy of SCE therapy for improving islet β cell function in patients with T1D through 12 months.
- 7.2.3 To evaluate markers of immune function in T1D patients after SCE therapy.

8 Study Design

8.1 General Design

This is a prospective, single arm, open-label, single-center pilot study to assess the safety, feasibility, and efficacy of SCE therapy for the treatment of patients with T1D. Up to 10 patients meeting eligibility criteria will be enrolled. Patients with T1D will be evaluated by the study principal investigator or co-investigators. Informed consent will be obtained at the initial screening visit (Visit 1). The initial screening visit will occur within 30 days of initiation of SCE therapy (**Table 3**). The second screening visit (Visit 2) will occur within 7 days of therapy. Subjects who meet all criteria will be scheduled for treatment. All enrolled subjects will receive treatment with the SCE system consisting of a single session of MNC collection by apheresis where 10 L (expected collection of ~10¹⁰ mononuclear cells) of blood will be processed on day -1. The MNC product will then be exposed over a 17-hour period of time to the SCE and on day 0 the product will be infused intravenously back to the patient. The infusion will take place in the Outpatient Transplant Facility at John Theurer Cancer Center (JTCC) or Inpatient at Hackensack University Medical Center (HUMC) on the stem cell transplantation or cellular therapy unit. The infusion will be performed according to the standard operating procedure, titled “Name of Procedure: Infusion of Non-Frozen Hematopoietic Stem Cell (HSC) Products and Cytotoxic T Lymphocytes”. After finishing the infusion, the patients will be hospitalized at the main hospital of Hackensack University Medical Center for a 24-hours post-infusion observation. If the patients show the stable blood glucose, blood pressure, temperature, and normal vital signs, they can be discharged from the hospital after 24 hours. Subjects will be treated sequentially, with a minimum of one week between subjects for the first three subjects. All treated subjects will attend a safety visit on Day +7 ± 1 day. Follow-up visits will occur on 1st, 3rd, 6th, 9th, 12th, and 24th month (± 5 days) post-therapy. Subjects will be instructed to record daily insulin doses, sugar levels, and physical activities. After receiving the SCE therapy, patients’ daily insulin doses will be monitored and adjusted their own endocrinologist.

[figure not shown]

Figure 25. Outline the SCE therapy and follow-up. Ten participants will receive a single treatment with the SCE and follow-up studies, as described in above diagram. The preparation of CB-SC cultures and SCEs will be performed as previously described [1]. Briefly, human cord blood units derived from healthy allogeneic donors will be obtained from FDA-registered CORD : USE Cord Blood Bank (Orlando, FL). All cord blood samples will be screened for HIV 1/2, HBsAg, HBcAg, HCV, HIVNAT, STS, HBVNAT, HCVNAT, AbScr, HTLV I/II, West Nile, Chagas, and CMV, and only pathogen-free cord blood units will be used for clinical treatment. Human CB-SC will be generated as previously described [6,8]. Cord blood mononuclear cells will be plated in serum-free culture medium (Lonza, Walkersville, MD) and incubated at 37°C, in 8% CO₂. After 2-3 weeks, CB-SC growing at 80% confluence will be prepared for clinical trial. One Educator device will be generated from one cord blood unit, and used for one subject. After overnight treatment through the co-culture of MNC product with CB-SCs, the SCE (SCE)-treated MNC will be collected and infused intravenously (i.v.) back to the subject in 3 - 5 hours.

8.2 Primary Study Endpoint

The primary study endpoint will be the occurrence of treatment-related adverse effects. Adverse events that occur during therapy (especially those that necessitate temporary or permanent discontinuation of therapy) and over the 12-month follow-up period will be assessed.

8.3 Secondary Study Endpoints

8.3.1 Feasibility endpoints:

- 8.3.1.1 The number of patients who were unable to complete SCE Therapy. Any non-adverse event related reasons for discontinuation of therapy will be recorded (eg: technical problems with the SCE system).
- 8.3.1.2 The number of patients who are lost to follow-up prior to the 12-month follow-up visit.

8.3.2 Efficacy endpoints

- 8.3.2.1 Area under the C-peptide curve (AUC) over the first 2 hours of a 3-hour mixed meal tolerance test (MMTT). The AUC at 12-months and changes over time will be assessed.
- 8.3.2.2 Peak C-peptide levels over a 3-hour MMTT. The peak C-peptide level at 12-months and changes over time will be assessed.
- 8.3.2.3 Basal C-peptide levels at 12-months and changes over time will be assessed.
- 8.3.2.4 Daily insulin requirements
- 8.3.2.5 Change in HbA1C levels over time
- 8.3.2.6 Changes in auto-antibody levels over time

8.3.3 Exploratory endpoints

- 8.3.3.1 Measurements of regular immune cell markers at baseline, 1, 3, 6, 9, 12, and 24 months
- 8.3.3.2 Flow cytometry of memory T cell markers at baseline, 1, 3, 6, 9, 12, and 24 months

Table 3. Schedule of Events

	Visit 1	Visit 2	Visit 3	Visit 4	Visit 5	Visit 6	Visit 7	Visit 8	Visit 9	Visit 10	Visit 11	Visit 12
PROCEDURE	Within 30 Days of Cord Blood Order	Day -7 to -1	Day -7 to -1	Day 0	Day +1 to +2	Day +7 ± 1 day	Month 1 ± 5 days	Month 3 ± 5 days	Month 6 ± 5 days	Month 9 ± 5 days	Month 12 ± 5 days	Month 24 ± 5 days
Informed Consent	x											
Verify Inclusion/Exclusion Criteria	x											
Vital Signs (Ht/Wt/Temp/BP/Hr/RR)	x				x		x	x	x	x	x	x
Medical History	x				x		x	x	x	x	x	x
Physical Exam	x				x		x	x	x	x	x	x
Venous assessment for apheresis	x											
LABS												
CBC	x				x		x	x	x	x	x	x
CMP	x					x	x	x	x	x	x	x
ABO Blood Typing Test	x											
Infectious disease testing (HIV, HTLV, Hep B, cAB, Hep C ab.	x											
HbA1C	x					x	x	x	x	x	x	x
Serum Pregnancy Test	x	x				x	x	x	x	x	x	x
Auto-antibodies (IAA, IA2, GAD, ZnT8)	x					x	x	x	x	x	x	x
Fasting C-peptide level	x	x	x	x	x	x	x	x	x	x	x	x
Fasting Blood Glucose Level	x	x	x	x	x	x	x	x	x	x	x	x
Fasting plasma pro-insulin level				x			x	x	x	x	x	x
Insulin dose recording	x					x	x	x	x	x	x	x
EKG	x											
METABOLIC STATUS												
Mixed meal tolerance test		x					x	x	x	x	x	x
Pro-Insulin level		x					x	x	x	x	x	x
Glucagon levels		x					x	x	x	x	x	x
Daily Insulin Doses: Patient Diary												
Daily Glucose Levels: Patient Diary												
IMMUNE MARKERS												
CD4 ⁺ CD25 ⁺ CD127 ^{low} /Tregs		x					x	x	x	x	x	x
CD4 ⁺ CD45RO ⁺ CCR7 ⁺ T _{CM} cells		x					x	x	x	x	x	x
Continuous												
Daily Glucose Levels: Patient Diary												

Table 3. Schedule of Events

	Visit 1	Visit 2	Visit 3	Visit 4	Visit 5	Visit 6	Visit 7	Visit 8	Visit 9	Visit 10	Visit 11	Visit 12
PROCEDURE	Within 30 Days of Cord Blood Order	Day -7 to -1	Day 0	Day +1 to +2	Day +7 ±1 day	Month 1 ± 5 days	Month 3 ± 5 days	Month 6 ± 5 days	Month 9 ± 5 days	Month 12 ± 5 days	Month 24 ± 5 days	
CD4 ⁺ ICOS ⁺ and CD8 ⁺ ICOS ⁺ T cells	x					x	x	x	x	x	x	x
IL-1, TNF α , IL-17	x					x	x	x	x	x	x	x
IL-10 and TGF – β 1	x					x	x	x	x	x	x	x
Th1/Th2 cytokines (IL4, IL5, IL12, IL13)	x					x	x	x	x	x	x	x
PLATELET MARKERS												
Platelet function testing	x					x	x	x	x	x	x	x
CD41 ⁺ CD42 ⁺ CD270 ⁺ CD274 ⁺ Galectin ⁺	x					x	x	x	x	x	x	x
TREATMENT												
Apheresis				day -1	cell infusion							
SAFETY ASSESSMENTS												
Phone call for safety follow-up					x	x				Continuous		
Concomitant med monitoring											Continuous	
Adverse Event monitoring												

9 Subject Selection and Withdrawal

This study will enroll a total of 10 subjects who meet the following eligibility criteria.

9.1 Inclusion Criteria

- 1) Adult patients (≥ 18 years)
- 2) Must have a diagnosis of type 1 diabetes mellitus based on the 2015 American Diabetes Association criteria for the Clarification and Diagnosis of diabetes.
- 3) Must have a blood test confirming the presence of at least one autoantibody to pancreatic islet β Cells (IAA, IA2, GAD 65, ZnT8).
- 4) Fasting C-peptide level ≥ 0.3 ng/ml
- 5) HbA1C $< 10\%$ at enrollment
- 6) Recent diagnosis (within two years of enrollment)
- 7) Adequate venous access for apheresis
- 8) Must be equipped with a continuous glucose monitoring system (CGMS)
- 9) Ability to provide informed consent
- 10) For female patients only, willingness to use FDA-recommended birth control (<http://www.fda.gov/downloads/ForConsumers/ByAudience/ForWomen/FreePublications/UCM356451.pdf>) until 6 months post treatment.
- 11) Must agree to comply with all study requirements and be willing to complete all study visits

9.2 Exclusion Criteria

Potential subjects meeting any of the following criteria will be excluded from participation:

- 1) AST or ALT $2 \geq x$ upper limit of normal.
- 2) Abnormal bilirubin (total bilirubin > 1.2 mg/dL, direct bilirubin > 0.4 mg/dL)
- 3) Creatinine ≥ 2.0 mg/dl.
- 4) Known coronary artery disease or EKG suggestive of coronary artery disease unless cardiac clearance for apheresis is obtained from a cardiologist.
- 5) Known active infection such as Hepatitis B, Hepatitis C, or Human Immunodeficiency Virus (HIV)
- 6) Pregnancy assessed by a positive serum pregnancy test or breastfeeding mothers
- 7) Use of immunosuppressive medication within one month of enrollment including but not limited to prednisone, cyclosporine, tacrolimus, sirolimus, and chemotherapy.
- 8) Presence of any other autoimmune diseases (lupus, rheumatoid arthritis, scleroderma, etc.)
- 9) Anticoagulation other than ASA.
- 10) Hemoglobin < 10 g/dl or platelets < 100 k/ml
- 11) Is unable or unwilling to provide informed consent
- 12) Presence of any other physical or psychological medical condition that, in the opinion of the investigator, would preclude participation

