6.4.1.1 Feasibility and Safety of SCE Therapy

Fifteen T1D patients were enrolled (baseline characteristics presented in **Table 6**). Median age was 29 years (range, 15 to 41), and median diabetic history was 8 years (range, 1 to 21). Participants were randomly assigned to receive SCE therapy (n=12) or sham therapy (n=3). Each participant received one treatment. Based on fasting C-peptide levels (a by-product of insulin biosynthesis, as an indicator for islet β cell function), participants in the treatment group were characterized as having moderate T1D with some residual β cell function (n = 6, Group A) or severe T1D with no residual pancreatic islet β cell function (n = 6, Group B) (**Table 6**). All Control Group participants had moderate T1D.

No participants experienced any significant adverse events during the course of treatment. Most patients experienced mild discomfort during venipuncture and some soreness of the arm during aphaeresis, but discomfort and soreness resolved quickly following the conclusion of the procedure. Twenty-four hours post treatment, no significant difference was noted in white blood cell counts relative to baseline (Total white blood cell count: $6.95 \times 10^9/L \pm 1.98$ vs $6.39 \times 10^9/L \pm 1.72$, $p = 0.38$; Granulocytes: $3.79 \times 10^9/L \pm 1.43$ vs $3.66 \times 10^9/L \pm 1.05$, $p = 0.77$; Lymphocytes: $2.31 \times 10^9/L \pm 0.9$ vs $2.08 \times 10^9/L \pm 0.67$, $p = 0.40$; Monocytes: $0.49 \times 10^9/L \pm 0.13$ vs $0.46 \times 10^9/L \pm 0.10$, $p = 0.48$). Participants' body temperatures were not significantly changed during the two-day post-treatment observation ($36.44^\circ C \pm 0.24$ vs $36.5^\circ C \pm 0.22$, $n = 15$, $p = 0.35$). No changes were observed in blood cell count or temperature at the 12-week follow-up.

CB-SCs are tightly adherent [8,9] and not expected to escape the device. To confirm CB-SCs are completely retained in the Educator and not transferred to the patient, we examined cells leaving the device to check for stage specific embryonic antigen 3 (SSEA-3), a CB-SC-specific marker. Flow cytometry confirmed the absence of SSEA-3 in cells leaving the Educator [1]. These data indicate that the cells returned to the patients are autologous. Additionally, HLA matching is not required prior to SCE therapy because CB-SCs are not transferred to the patient and because CB-SCs have very low immunogenicity [8,9,11]. Thus, SCE therapy is a very safe approach.

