9.3 Subject Recruitment and Screening

Subjects will be recruited for the study by any of the investigators, co-investigators, endocrinologists, other medical professionals who treat Type 1 Diabetes. Patients may also be self-referred. If subjects consent to participate in the trial, diagnostic testing necessary to meet above inclusion or exclusion criteria will be performed. The list of screening requirements will include a regular blood count analysis, a blood test to confirm the presence of at least one autoantibody to pancreatic islet β cells, and other associated testing to exclude pregnancy, clinically significant liver, kidney, or heart disease. Patients will be referred to the Principal Investigator, [name], for the apheresis and re-infusion therapy portion of the protocol only. There will be a follow-up with a safety phone call on Day 1 or 2 after re-infusion and on Day 7 \pm 1. This will be performed by the research nurses.

Copies medical records from all visits to the JTCC will be sent to the treating physicians.

The rescreening of subjects who previously failed eligibility is allowable.

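### Exclusion 10 prints the platelet limit per millilitre, 1,000 times below the evident per-microlitre limit, so read literally it screens out no realistic candidate

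*Combined protocol and SAP*

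**What the plan says.** Section 9.2 opens its list with the rule "Potential subjects meeting any of the following criteria will be excluded from participation", so each item is sufficient alone. Item 10 reads "Hemoglobin < 10 g/dl or platelets < 100 k/ml".

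The count that feeds this criterion is taken at screening. Section 9.3 says "The list of screening requirements will include a regular blood count analysis", and both the Schedule of Events (Table 3) and Section 11.1 list a CBC at Visit 1. None of these gives a platelet cut-off. Table 3 also lists platelet function testing, again without a limit. Exclusion 10 is therefore the only numeric platelet limit in the documents.

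The general route to exclusion is item 12: "Presence of any other physical or psychological medical condition that, in the opinion of the investigator, would preclude participation". It carries no number.

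**The concern.** Read as printed, "platelets < 100 k/ml" sets a floor that no realistic candidate would fall below. The line looks like a working safety threshold but would not exclude a patient with marked thrombocytopenia.

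Every subject undergoes apheresis with about 10 L of blood processed (Sections 8.1, 10.2 and 10.4). If peripheral access proves insufficient on the day, Section 10.4 (Step 5) and Section 11.1 allow a femoral apheresis catheter, and Section 13.1.1 names bleeding at the site among the risks of a central catheter. Exclusion 9 bars anticoagulants but permits aspirin. The platelet count is thus the only numeric limit in the list that bears directly on bleeding risk.

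Safety is the primary endpoint. Under Sections 12.1 and 13.4, procedure-related grade 3 events in 2 patients end this 10-patient study. Eligibility text is also what monitors and auditors check against. As printed, enrolling someone with 40 k/µL would not breach criterion 10, and excluding that person under criterion 10 would have no support in the text.

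**Working it through.** The plan derives no figure here, so there is nothing to reproduce. The check is a unit conversion.

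**Inputs**

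- Printed limit: 100 k/ml (Section 9.2, exclusion 10), with k = 1,000.
- Presumed intended limit: 100 k/µL. This is an assumption; the documents do not state it.
- Conversions: 1 ml = 1,000 µL and 1 L = 1,000 ml.
- Scale check from Section 6.4.1.1, the earlier trial in type 1 diabetes: mean white cell count 6.95 × 10^9/L and mean monocyte count 0.49 × 10^9/L.

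**Printed limit**

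- 100 × 1,000 = 100,000 per ml
- 100,000 / 1,000 = 100 per µL
- 100,000 × 1,000 = 10^8 per L = 0.1 × 10^9/L

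**Presumed limit**

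- 100 × 1,000 = 100,000 per µL
- 100,000 × 1,000 = 100,000,000 per ml
- 100,000,000 × 1,000 = 10^11 per L = 100 × 10^9/L

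**Ratio:** 100 / 0.1 = 1,000.

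**What each reading excludes**

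| Platelet count | Per ml | Excluded as printed (< 100,000/ml) | Excluded at 100 k/µL |
|---|---|---|---|
| 1 k/µL | 1,000,000 | No | Yes |
| 10 k/µL | 10,000,000 | No | Yes |
| 50 k/µL | 50,000,000 | No | Yes |
| 99 k/µL | 99,000,000 | No | Yes |
| 150 k/µL | 150,000,000 | No | No |

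Of the 0 to 100 × 10^9/L interval that the presumed limit would exclude, the printed limit covers 0.1 / 100 = 0.1%. That is a share of the numeric range, not of candidates.

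**Scale check within the document**

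- White cells: 6.95 / 0.1 = 69.5, so the printed floor is about 1/70 of the reported mean.
- Monocytes: 0.49 / 0.1 = 4.9, so it is about 1/5 of that mean.

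A platelet floor below the usual count of a minor white cell fraction is not a plausible design choice. This supports reading the unit as an error.

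**The case against.** The strongest reply is that this is a slip that any clinician corrects on sight. No reader would act on 100 platelets per µL, a CBC is done at screening, and the numeric screen would in practice run at 100 k/µL. Harm would need several things together: a thrombocytopenic candidate, a literal reading, and no use of exclusion 12. Catheter bleeding would also need failed peripheral access on the day, despite inclusion 7 and the nurse's venous assessment. Exclusion 8 could catch some autoimmune thrombocytopenia as well. The documents give no platelet distribution, so the number wrongly admitted cannot be estimated and among 10 subjects may well be zero.

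These points stand as limits on the practical effect. They do not make the printed threshold right, and nothing elsewhere in the protocol corrects it.

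The second reply is that the PDF text may have been misread. The reading is imperfect: Section 10.4 (Step 5) shows the cell target as 1010 where Sections 8.1 and 10.2 show 10^10, and the AST/ALT criterion in Section 9.2 itself is disordered. Against this, micro signs survive elsewhere, for example in Section 6.3.2.2 and the Figure 24 legend. A simply dropped micro sign would also leave k/l; k/ml needs an m substituted for it. A misread is possible but not indicated, and a look at the source page would settle it.

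**Conclusion.** The concern holds. Taken literally, the platelet limit in exclusion 10 is 0.1 × 10^9/L, 1,000 times below the evident 100 × 10^9/L, and it is inoperative as a numeric screen. The hemoglobin limit is sound.

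The factor of 1,000 rests on the intended unit being per microlitre, which is inferred. That the printed limit is unworkable does not depend on this inference. The conclusion also assumes that the text was read correctly from the PDF.

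The likely effect on who is enrolled is small. The point deserves correction because the line is a safety threshold applied to every candidate before an invasive procedure.

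**What to change.** Check the line against the source page and have the sponsor confirm the limit. Then reword the platelet half of exclusion 10 as: platelets < 100 k/µL (100 × 10^9/L). Giving both units removes any doubt about scale.

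The cost is a unit correction in one line. Screening already includes the CBC, so no procedure is added, and sample size, visit schedule and analysis do not change.

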9.3 Subject Recruitment and Screening

Subjects will be recruited for the study by any of the investigators, co-investigators, endocrinologists, other medical professionals who treat Type 1 Diabetes. Patients may also be self-referred. If subjects consent to participate in the trial, diagnostic testing necessary to meet above inclusion or exclusion criteria will be performed. The list of screening requirements will include a regular blood count analysis, a blood test to confirm the presence of at least one autoantibody to pancreatic islet β cells, and other associated testing to exclude pregnancy, clinically significant liver, kidney, or heart disease. Patients will be referred to the Principal Investigator, [name], for the apheresis and re-infusion therapy portion of the protocol only. There will be a follow-up with a safety phone call on Day 1 or 2 after re-infusion and on Day 7 \pm 1. This will be performed by the research nurses.

Copies medical records from all visits to the JTCC will be sent to the treating physicians.

The rescreening of subjects who previously failed eligibility is allowable.

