10.3 Method for Assigning Subjects to Treatment Group

There is only one treatment group. Based on fasting C-peptide levels (a by-product of insulin biosynthesis, with normal reference range 0.8 – 3.1 ng/mL), as an indicator for islet β cell function, all participants will be characterized and assigned as one group having moderate T1D with some residual β cell function (fasting C-peptide level ≥ 0.3 ng/mL, n = 10). Each participant will receive one treatment.

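### HbA1C and autoantibodies have no pre-treatment value except the one that decides eligibility, so some regression to the mean is built into two single-arm change endpoints

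*Combined protocol and SAP*

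**What the plan says.** Section 9.1 sets three entry criteria on laboratory values: HbA1C below 10% at enrollment, "Fasting C-peptide level ≥ 0.3 ng/ml", and, for autoimmunity, "Must have a blood test confirming the presence of at least one autoantibody to pancreatic islet" β cells, with four antibodies named. Section 9.3 adds, in one sentence, that "The rescreening of subjects who previously failed eligibility is allowable". It gives no number of attempts, interval, list of repeatable criteria or rule for which value counts.

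In Table 3, the HbA1C and autoantibody rows are each marked at Visit 1 and then not until Visit 6 (Day +7). Section 11 agrees: autoantibody testing is listed under Visit 1, while Visit 2 describes only a pregnancy test and the meal test. C-peptide is handled differently. The row "Mixed meal tolerance test" has its first mark at Visit 2 (Day -7 to -1), and fasting C-peptide is marked at every visit.

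Endpoints 8.3.2.5 and 8.3.2.6 are change in HbA1C and "Changes in auto-antibody levels over time". Section 12.1 models HbA1C from baseline to 24 months with a repeated-measures mixed model, but ties baseline to no visit or screening attempt. It specifies no analysis for autoantibodies.

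**The concern.** When a measurement must fall on one side of a cut-off for a patient to enter, the recorded value is on average displaced towards the passing side, because near-threshold patients enter only when their error is favourable. If the same value then serves as baseline, later values tend to drift back. A concurrent control arm would show the same drift and cancel it, but this trial has one open-label arm.

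The two endpoints are pushed in opposite directions. HbA1C has an upper limit, so the passing value is too low, follow-up drifts up and any benefit is slightly understated. The autoantibody criterion requires a positive result, so a chance positive tends to fall later. That could be read as the reversal of autoimmunity that the protocol expects.

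The baseline may also be old. Section 11.1 and Table 3 allow Visit 1 up to 30 days before the cord blood order, and 10.4 gives 10 to 20 days of culture. That makes 30 + 10 = 40 to 30 + 20 = 50 days, before any delivery time. Section 8.1 instead places Visit 1 within 30 days of therapy. Even on that reading the value can be about a month old.

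**Working it through.** The plan gives no figure for this effect, so there is nothing of its own to reproduce.

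**Inputs.** The cut-off of 10% is from 9.1. Within-person HbA1C SD (s) is not in the documents and is assumed to be 0.2, 0.3 or 0.5 point. Two candidate populations of usual HbA1C are assumed: mean/SD 8.73/2.49, borrowed from Group A (six patients) of the earlier Chinese trial in 6.4.1.2, and 8.0/1.5, a pure assumption. Errors are taken as normal and independent between screens.

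**Step 1: one borderline candidate.** For usual value T, put a = (10 − T)/s. The chance of passing one screen is p = Φ(a), and of passing within k screens 1 − (1 − p)^k. The passing value differs from T by −s·φ(a)/Φ(a) on average. At T = 10.2:

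| s | p, one screen | within three screens | passing value minus T |
|---|---|---|---|
| 0.2 | 0.159 | 0.404 | −0.31 |
| 0.3 | 0.252 | 0.582 | −0.38 |
| 0.5 | 0.345 | 0.718 | −0.53 |

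The last column does not contain k. A borderline patient who passes at the first attempt has the same displaced baseline as one who passes at the third. The displacement comes from using one value for both entry and baseline. Rescreening only changes how many such patients enter.

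**Step 2: the whole cohort.** One million candidates were simulated per setting. Everyone who failed was rescreened up to the limit, so rescreening is used to the full. The table gives the mean of recorded baseline minus usual HbA1C among those enrolled.

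| Population | s | one screen | up to three | added by rescreening | usual HbA1C ≥ 10% (one; three) |
|---|---|---|---|---|---|
| 8.73/2.49 | 0.2 | −0.008 | −0.014 | −0.006 | 1.6%; 3.4% |
| 8.73/2.49 | 0.3 | −0.018 | −0.031 | −0.013 | 2.3%; 4.9% |
| 8.73/2.49 | 0.5 | −0.050 | −0.082 | −0.032 | 3.8%; 7.7% |
| 8.0/1.5 | 0.2 | −0.004 | −0.008 | −0.004 | 0.9%; 1.8% |
| 8.0/1.5 | 0.3 | −0.011 | −0.018 | −0.007 | 1.2%; 2.6% |
| 8.0/1.5 | 0.5 | −0.031 | −0.049 | −0.018 | 1.8%; 3.8% |

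With up to three screens the baseline is about 0.01 to 0.08 point too low, of which rescreening contributes at most about 0.03. Five screens for every failure would stretch the total to 0.010 to 0.099. At three screens the expected number of patients in ten whose usual HbA1C is 10% or more is 0.18 to 0.77.

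**Step 3: autoantibodies.** A truly negative candidate tested on four independent assays, each with false-positive rate f, passes within k screens with probability 1 − (1 − f)^(4k). For f = 1% this is 3.9% once and 11.4% within three; for f = 2% it is 7.8% and 21.5%. These rates are assumed, and the results are chances of entry for one kind of candidate. They do not give the bias in the endpoint. That would need the number of such candidates, the assay cut-offs and the within-person variability, none of which the documents state.

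**The case against.** The strongest reply is that the effect is small and lies away from what matters most. The primary endpoint is treatment-related adverse events, which needs no laboratory baseline. Section 12.2 names change in C-peptide secretion as the primary efficacy endpoint. Its meal-test baseline is taken at Visit 2, and fasting C-peptide is drawn again at Visits 2 and 3. The HbA1C bias runs against the treatment and cannot create a false benefit. Candidates must already have diagnosed type 1 diabetes, so truly antibody-negative candidates may be few, and a persistent cross-reaction would not fall on repeat. All of this stands. It limits the size of the point but does not supply a baseline free of selection.

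A reader might also infer that 9.3 lets sites retest until a value passes, so that the entry thresholds erode. The documents do not support that. The section is silent on limits; it does not invite repeat testing. The two-year diagnosis window and the Visit 1 timing restrict attempts, and better glycaemic control is a legitimate reason to return. Averaging a failed and a later value would conflict with a criterion set at enrollment: 11.6% followed by a genuine 8.8% averages 10.2% and would exclude a patient who meets 9.1. After a rescreen the failed value also exists, so Visit 1 is the only scheduled pre-treatment value, not necessarily the only one on record.

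**Conclusion.** The gap is real and modest. For HbA1C and autoantibodies, the value that decides eligibility is also the only scheduled pre-treatment value, and 12.1 does not say what baseline means. Under the assumed SDs, populations and up to three screens, mean baseline HbA1C is about 0.01 to 0.08 point too low, to the treatment's disadvantage. For autoantibodies the direction would favour the treatment and the size is unknown. Rescreening enlarges the effect slightly, but banning it would leave the effect in place.

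A larger figure is tempting. A patient with usual HbA1C 10.3% and s of 0.3 or 0.4 who passes has a mean recorded value of 9.84% or 9.77%, about half a point too low. One to three such patients in ten would shift the mean change by 0.46/10 ≈ 0.05 to 3 × 0.53/10 ≈ 0.16 point. Nothing in the documents supports a count of one to three, and the simulation puts it below one in ten. Nor is the whole cohort's baseline a selected extreme. The displacement concerns patients near a cut-off.

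**What to change.** In Table 3, add HbA1C and the autoantibody panel to the blood draw that Visit 2 already requires for the meal test and immune markers, taken before apheresis. In 12.1, name Visit 2 as the analysis baseline for endpoints 8.3.2.5 and 8.3.2.6. Use Visit 1 values for eligibility only, and do not let the Visit 2 values feed back into eligibility, or the selection returns. Keep every screening value on the CRF, including failed ones. Section 9.3 need not change for this purpose: a cap on rescreening would be a useful clarification but is not required.

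The cost is two extra assays per patient (HbA1C and the antibody panel) on blood already being drawn, plus wording in Table 3 and 12.1. The change also brings the baseline to within Day -7 to -1 of treatment.
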